## **11 ETHICAL, LEGAL AND ADMINISTRATIVE ASPECTS**

### **11.1 Good Clinical Practice**

The procedures set out in this study protocol are designed to ensure that the Sponsor and investigator abide by the principles of the Good Clinical Practice guidelines of the International Council for Harmonization (ICH), and of the Declaration of Helsinki. The study also will be carried out in keeping with local legal requirements.

### **11.2 Informed Consent**

Before the first study-specific screening procedure can be performed, informed consent must be obtained from each subject (or his/her legally authorised representative) according to the regulatory and legal requirements of the participating country (i.e., the Declaration of Helsinki, ICH GCP, and other applicable local regulations). This consent form must be approved by responsible IEC and must be signed and dated by subject and authorised consentor and retained by the investigator as part of the study records. The investigator will not undertake any investigation specifically required only for the clinical study until valid consent has been obtained. The terms of the consent and when it was obtained must also be documented in the subjects' medical records.

If a protocol amendment is required, the informed consent form may need to be revised to reflect the changes to the protocol. If the consent form is revised, it must be reviewed and approved by the appropriate IEC and signed by all subjects subsequently enrolled in the study as well as those currently enrolled in the study.

### **11.3 Protocol Approval and Amendment**

Before the start of the study, the study protocol and/or other relevant documents will be approved by the IEC/ Competent Authorities, in accordance with local regulatory requirements. The Sponsor must ensure that all ethical and regulatory requirements have been met before the first subject is enrolled in the study.

This protocol is to be followed exactly. To alter the protocol, amendments must be written, receive approval from the appropriate personnel, and receive IEC/Competent Authority approval prior to implementation (if appropriate), unless a protocol deviation is required in the event of an urgent safety need.

All amendments will be distributed to all protocol recipients, with appropriate instructions.

### **11.4 Archiving Study Records**

According to ICH guidelines, essential documents should be retained for a minimum of 2 years after the last approval of a marketing application in an ICH region and until there are no pending or contemplated marketing applications in an ICH region or at least 2 years have elapsed since the formal discontinuation of clinical development of the investigational product. However, these documents should be retained for a longer period if required by the applicable regulatory requirements.

Records and documents, including signed ICFs, pertaining to the conduct of this study must be retained by the investigator for 15 years after study completion unless local

regulations or institutional policies require a longer retention period. No records may be destroyed during the retention period without the written approval of the sponsor. No records may be transferred to another location or party without written notification to the sponsor.

### **11.5 Premature Termination of the Study**

If the Investigator, the Sponsor, or the Medical Monitor becomes aware of conditions or events that suggest a possible hazard to subjects if the study continues, the study may be terminated after appropriate consultation between the relevant parties. The study may also be terminated early at the Sponsor's discretion in the absence of such a finding.

Conditions that may warrant termination include, but are not limited to:

- The discovery of an unexpected, significant, or unacceptable risk to the subjects enrolled in the study;
- Failure to enrol subjects at an acceptable rate;
- A decision on the part of the Sponsor to suspend or discontinue development of the drug.

### **11.6 Confidentiality**

All study findings and documents will be regarded as confidential. The investigator and members of his/her research team must not disclose such information without prior written approval from the Sponsor.

The anonymity of participating subjects must be maintained. Subjects will be identified on eCRFs and other documents by their subject number allocated in the trial, not by name. Documents that identify the subject (e.g., the signed informed consent, subject identification list) must be maintained by the investigator as part of the ISF in a secure and confidential manner.

### **11.7 Liability and Insurance**

The Sponsor will take out reasonable third-party liability insurance cover in accordance with all local legal requirements. The civil liability of the investigator, the persons instructed by him and the hospital, practice or institute in which they are employed and the liability of the Sponsor with respect to financial loss due to personal injury and other damage that may arise as a result of the carrying out of this study are governed by the applicable law.

The Sponsor will arrange for subjects participating in this study to be insured against financial loss due to personal injury caused by the pharmaceutical products being tested or by medical steps taken in the course of the study.

### **11.8 Publication Policy**

By signing the study protocol, the investigator agrees with the use of results of the study for the purposes of national and international registration, publication and information for medical and pharmaceutical professionals. If necessary, the

authorities will be notified of the investigator's name, address, qualifications and extent of involvement.

An investigator shall not publish any data (poster, abstract, paper, etc.) without having consulted with the Sponsor in advance and gained written approval.

**APPENDIX 2: OVERALL SCHEDULE OF ASSESSMENTS**

	Visit 1 Screening Visit	Visit 2 Baseline Visit	Visit 3	Visit 4 EoT Visit	Visit 5 Follow-up or Early Termination Visit*
Activity	Enrolment	Treatment start	Treatment	End of Treatment	Follow-up
Day	-21 to -14	1	15 (±2 days)	28 (-2/+1 days)	42-49
Confirmation of Signed Informed consent	X				
Demographics	X				
Medical and surgical history	X				
Concomitant medication	X	X	X	X	X
Physical examination	X	X a	X a	X a	X
Nailfold capillaroscopy	X b				
Vital signs (BP, heart rate)	X	X	X	X	X
Weight/height	X				X c
ECG	X	X d	X		X
Clin chem and haematology	X	X	X	X	X
Thyroid hormones (free T3/T4, tot T4, TSH)	X				
Urinalysis – dipstick	X	X	X	X	X
SSc-related autoantibodies e	X				
Pregnancy test (WOCBP) f	X	X		X	X p
Inclusion/exclusion criteria	X	X			
Hepatitis B, C, HIV-test	X				
Drug screen g	X	X		X	
eDiary	X h				X i
ASRAP questionnaire (PRO)		X	X	X	X
Global Impression of Change (Subject/Physician)				X	
Adverse events	X	X	X	X	X
Randomisation		X			
IMP administration at site j		X		X	
IMP dispense to subjects		X	X		

	Visit 1 Screening Visit	Visit 2 Baseline Visit	Visit 3	Visit 4 EoT Visit	Visit 5 Follow-up or Early Termination Visit*
Activity	Enrolment	Treatment start	Treatment	End of Treatment	Follow-up
Day	-21 to -14	1	15 (±2 days)	28 (-2/+1 days)	42-49
IMP collection and compliance			X	X	
PK sampling (sparse)		X	X	X	
AA metabolites, and urine creatinine k		X		X	
Blood biomarker sampling l		X		X	
Biobank samples – urine and blood		X		X	
Assessments below will be conducted at pre-selected sites					
Finger temperature		X			
Cold challenge, thermography		X m		X	
PK sampling (rich)				X	
PGE 2 levels in whole blood		X		X	
Platelet activation (FACS) n		X		X	
Microvascular volume (D-OCT)		X o	X	X o	X

\* Also, the Early Termination visit, if applicable.

- Abbreviated examination (minimally to include statement regarding DUs).
- Could be performed at Visit 2 if not feasible at Visit 1.
- Only weight (not height) to be recorded at this visit.
- Two ECG assessments will be performed, one pre- and another 170 min post-IMP administration.
- Analysis of antinuclear antibodies (ANA), Scl-70 antibody (anti-topoisomerase I) and anti-centromere antibodies (ACA)
- Urine dipstick pregnancy test in WOCBP. At Visit 1, FSH assessment will be performed for women not of childbearing potential.
- For presence of alcohol or prohibited substances, e.g. cocaine
- Subjects will be given access to an eDiary and given instructions on how to use it at study enrolment. The eDiary will include the RCS, NRS pain scale, record of attacks (start time and finish time and date), IMP administration timepoints and reminders to subject.
- eDiaries will be completed for the final time and then “closed” so that no further data are entered.
- IMP administered together with food at the study site.
- Subjects bring a urine sample (first urination of the day) from home to the study site in the container provided.
- Predefined biomarkers (including hsCRP, Endothelin-1, sE-selectin, xICAM1, TNF, IL-1b, IL-4, IL-6, IL-10, s-PECAM1 CXCL-4, CD40L and von Willebrand factor).
- Two cold challenges will be performed, one pre- and another 180 mins post-IMP administration, see Appendix 2.1.
- Analysis of surface markers of platelet activation performed at a local laboratory.
- Two D-OCT assessments will be performed, one pre- and another 175 mins post-IMP administration
- WOCBP will receive a home pregnancy test to be used 35-40 days after their last dose of IMP.

**APPENDIX 3: DETAILED SCHEDULE OF ASSESSMENTS – VISIT 2**

	≥30-0	Minutes (time window +/- 5 minutes, exact time recorded in eCRF)										
		0	30	60	90	120	150	170	175	180 (180-195)	200	
Arrival at site	X											
Morning urine sample collection (AA-metabolites, urine creatinine)	X											
Physical examination (minimum DU)	X											
Vital signs (BP, heart rate)	X											
ECG	X							X				
Nailfold capillaroscopy (if not performed at Visit 1)	(X)											
Pregnancy test (WOCBP) (urine dipstick)	X											
Drug Screen a	X											
Urinalysis (dipstick)	X											
Review of eDiary compliance	X											
Concomitant medication	X											
Inclusion/exclusion criteria	X											
Clin chem and haematology	X											
Biomarkers (blood) b	X											
Collect blood and urine for Biobank	X											
Randomisation	X											
Adverse Event	X c											
IMP administration		X d										
ASRAP questionnaire			X									
PK sampling sparse											X	
IMP dispensation												X
Assessments below will be conducted at pre-selected sites												
PGE2 levels in whole blood	X											
Platelet activation (FACS) e	X											
Microvascular volume (D-OCT)	X										X	

a. For presence of alcohol or prohibited substances, e.g. cocaine

b. hsCRP, Endothelin-1, sE-selectin, ICAM1, TNF, IL-1b, IL-4, IL-6, IL-10, s-PECAM1 CXCL-4, CD40L and von Willebrand factor

- c. AE collection reflecting the time from the previous visit as well as any AEs experienced during the day.
- d. IMP will be administered with food.
- e. Analysis of surface markers of platelet activation performed by FACS analysis at a local laboratory.

**DETAILED SCHEDULE OF ASSESSMENTS COLD CHALLENGE/THERMOGRAPHY – VISIT 2**

The detailed schedule of assessment below describes the **additional** assessments at Visit 2 if the subject is enrolled to Cold Challenge.

	Session 1 										Session 2 				
	Minutes (time window +/- 5 minutes, exact time recorded in eCRF)														
	0 (0-15)	30	80	100	120 	0	30	60	90	120	150	170	175	180 (180-195)	200
Cold Challenge / Thermography															
Finger temperature															
Cold challenge with thermography every 15 seconds	X														
Thermography			X	X	X	X	X	X	X	X	X	X	X	X	

 Session 1 is conducted after randomization and prior to IMP administration.

 Session 2 starts at the same time as IMP administration, see DETAILED SCHEDULE OF ASSESSMENTS – VISIT 2.

 Estimated that skin temperature has returned to normal at 120 minutes, otherwise wait until it has returned to normal.

**APPENDIX 4: DETAILED SCHEDULE OF ASSESSMENTS – VISIT 4**

Assessment	Minutes (time window +/- 5 minutes, exact time recorded in eCRF)												
	≥30-0	-5	0	30	60	90	120	150	175	180 (180-195)	240	360	480
Arrival at site	X												
Morning urine sample collection (AA-metabolites, urine creatinine)	X												
Physical examination (minimum DU)	X												
Vital signs (BP, heart rate)	X												
Drug screen a	X												
Urinalysis (dipstick)	X												
Pregnancy test (WOCBP) (urine dipstick)	X												
Review of eDiary	X												
Collect blood and urine for Biobank	X												
Adverse Event b	X												
Concomitant medication	X												
IMP collection	X												
ASRAP questionnaire				X									
Clin chem and haematology	X												
Biomarkers (blood) c	X												
Patient Global Impression of Change d	X												
Physician Global Impression of Change	X												
PK sample, sparse		X								X e			
IMP administration f			X										

Assessment	Minutes (time window +/- 5 minutes, exact time recorded in eCRF)												
	≥30-0	-5	0	30	60	90	120	150	175	180 (180-195)	240	360	480
Assessments below will be conducted at pre-selected sites													
Thermography		X											
Cold challenge with thermography every 15 seconds										X			
PK sample, rich s		X		X	X	X	X		X		X	X	X
PGE 2 levels in whole blood	X												
Platelet activation (FACS) h	X												
Microvascular volume (D-OCT)	X								X				

- For presence of alcohol or prohibited substances, e.g. cocaine
- AE collection for past study period as well as any experienced during the day.
- hsCRP, Endothelin-1, sE-selectin, ICAM1, TNF, IL-1b, IL-4, IL-6, IL-10, s-PECAM1 CXCL-4, CD40L and von Willebrand factor.
- If not already completed by subjects in the morning at home (diary).
- The PK sampling for subjects enrolled to cold challenge assessment is to be drawn at 175 mins, for all other subjects at 120 mins.
- IMP will be administered with food.
- The schedule includes sparse PK sampling that is also drawn from subjects enrolled in rich PK. If feasible, a PK sample should be drawn at 480 min, or as late as possible.
- Analysis of surface markers of platelet activation performed by FACS.

## **APPENDIX 5: COLD CHALLENGE AND THERMOGRAPHY**

### *Preparation for cold challenge*

All measurements will be performed in a temperature-controlled room ( $23^{\circ}\text{C} \pm 2^{\circ}\text{C}$ ) or a temperature-monitored room. The room temperature will be recorded in order to monitor any changes and their effects on the data. Subjects will be requested to wear light clothing and must refrain from vigorous exercise, caffeine and alcohol for at least 4 hours prior to the assessment. Upon arrival subjects will be seated comfortably in the temperature-controlled (or temperature-monitored) room for 20 minutes and acclimatised.

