### *Thermography*

Thermography images will be securely transferred electronically to the University of Manchester for automated analysis. The region of interest is defined as 2 dorsal regions: one on the dorsum of each hand and all 8 distal phalanges (excluding thumbs). At baseline before cooling, a distal dorsal difference (DDD) is defined for all 4 fingers on each hand in relation to the dorsum of the same hand (4 values for each hand, i.e., 8 in total). These are then averaged to give one DDD per hand or one for both hands. During and after cold challenge only the fingers are assessed. At each time point, the value for the 8 fingers can be plotted individually, but the areas under the curve (AUC) and maximum values are averaged for all 8 fingers. Thus, providing one DDD and one AUC and MAX per subject per cold challenge. This will be performed in a semi-automated way using software (based on observer-defined regions).

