1.2 Secondary objective

Table 1.1: Study Objectives and Endpoints

Objectives	Endpoints

Secondary:
	
Secondary:
 
 • Mean change from baseline to week 4 in peripheral blood flow prior to

Statistical Analysis Plan	Version 2.0		Page 9 of 10
Sponsor	Gesynta Pharma AB	Protocol No	GS-2001

Objectives	Endpoints
To determine the efficacy of GS-248 on peripheral vascular blood flow in subjects with SSc and RP.	cold challenge and IMP administration. 
 • Mean change in peripheral blood flow from pre-IMP to post-IMP administration at Visit 2. • Mean change in recovery of peripheral blood flow after cold challenge from pre-IMP to post-IMP administration at Visit 2. • Mean change from baseline to week 4 in recovery of peripheral blood flow after cold challenge.

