5.1.4 Descriptive statistics

Descriptive statistics will be presented for the number of RP attacks by visit and mean change between visit 4 and baseline, using observed data only.

The analysis of the primary endpoint will be performed using analysis of covariance, AN-COVA), including the stratification factor (vasodilatory treatment i.e., Ca-blockers, PDE-5 inhibitors, or no background vasodilatory treatment) and treatment as fixed factors and baseline levels as a covariate in the model.

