5.3 Exploratory objectives and endpoints

5.3.1 Patient Global Impression of Change at week 4.

Patient Global Impression of Change at week 4 will be presented for the number and percentage of subjects providing the categorized week 4 responses for each treatment group.

The statistical analysis will consist of a Cochran-Mantel-Haenszel analysis comparing treatment groups adjusting for the stratification factor.

5.3.2 Physician Global Impression of Change at week 4.

Physician Global Impression of Change at week 4 will be presented for the number and percentage of subjects providing the categorized week 4 responses for each treatment group.

The statistical analysis will consist of a Cochran-Mantel-Haenszel analysis comparing treatment groups adjusting for the stratification factor.

5.3.3 Mean change in ASRAP Questionnaire score from baseline to week 4

The ASRAP questionnaire score (reporting on the past 7 days) results for each patient in the ASRAP total score, the sum of all items scores.

The analysis of the Mean ASRAP Questionnaire total score will be similar to the analysis of the primary efficacy endpoint using observed data.

Statistical Analysis Plan	Version 2.0		Page 22 of 23
Sponsor	Gesyntha Pharma AB	Protocol No	GS-2001

Descriptive statistics of the observed cases and mean change from baseline will be created for the ASRAP Questionnaire total score at baseline, week 2, week 4 and at follow-up.

5.3.4 Mean change from baseline to week 4 in peripheral blood flow prior to cold challenge and IMP administration

The following parameters for peripheral blood flow prior to cold challenge are defined:

- Mean temperature of all eight fingers prior to cold challenge (MTEMPALL)
- Mean Distal Dorsal Difference (DDD) of all eight fingers prior to cold challenge (MDDDF)

Descriptive statistics of the observed cases and change from baseline will be created for these parameters at baseline (first assessment at visit 2, $t < 0$) and week 4 ($t = -5$ min).

The analysis of the peripheral blood flow will be similar to the analysis of the primary efficacy endpoint using observed data.

5.3.5 Mean change in peripheral blood flow from pre-IMP to post-IMP administration at Visit 2

The following parameters for peripheral blood flow from pre-IMP to post-IMP administration are defined:

- Mean temperature of all eight finger after IMP administration but prior to cold challenge at visit 2 (MTEMPALL)

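### Room temperature is recorded to follow its effect on the thermography data, but none of the four blood-flow analyses uses it: an avoidable loss of precision of unknown size, not a bias

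*Protocol*

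**What the plan says.** Protocol Appendix 5 (preparation for cold challenge) asks for all measurements to be made in a temperature-controlled room at 23 ± 2 °C "or a temperature-monitored room". It continues: "The room temperature will be recorded in order to monitor any changes and their effects on the data". Subjects acclimatise for 20 minutes, and the cold challenge protocol in the same appendix specifies rewarming at 23 ± 2 °C ambient.

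The thermography part of Appendix 5 gives one parameter a reference within the hand: before cooling, "a distal dorsal difference (DDD) is defined for all 4 fingers on each hand in relation to the dorsum of the same hand". The recovery parameters have none: "During and after cold challenge only the fingers are assessed".

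SAP 5.3.4 to 5.3.7 define mean finger temperature and mean DDD before the challenge, and LN(AUC) and LN(maximum) after it. Each of the four sections closes with the same instruction: "The analysis of the peripheral blood flow will be similar to the analysis of the primary efficacy endpoint using observed data". SAP 5.1.4 sets out that model: the stratification factor and "treatment as fixed factors and baseline levels as a covariate in the model".

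Neither document gives a covariate, summary, exclusion rule or sensitivity analysis that uses room temperature. Under the general rule in SAP section 4 it would at most be listed.

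**The concern.** The protocol gives a reason for recording the room temperature, and the SAP does not act on it. Skin temperature of the fingers is the outcome, so some dependence on the surrounding air is plausible. The baseline covariate can absorb part of the room effect at the baseline session, but none of it at the later one.

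What stays in the residual differs by endpoint:

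- **SAP 5.3.4 and 5.3.7** compare Visit 2 with Visit 4, about four weeks apart. Differences in the room between visits enter here.
- **SAP 5.3.5 and 5.3.6** compare sessions within Visit 2. Only drift during the day can enter.

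At stake is the precision of the four endpoints that carry the whole secondary objective, "To determine the efficacy of GS-248 on peripheral vascular blood flow in subjects with SSc and RP". They are measured in an estimated 50 subjects, and neither document gives a power calculation for that subset.

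**Working it through.** **The plan's own figure.** The only sample-size figure is 26 per group, for Raynaud attacks (difference 8.0, SD 10.0, two-sided 0.05, 80% power). An exact t-test gives 25.5, rounded up to 26, so it reproduces. It says nothing about thermography, for which the documents give no SD, effect size or room-temperature slope. The rest is illustration under stated assumptions.

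**Inputs from the documents.** Room range 21-25 °C (23 ± 2); about 50 subjects, so about 25 per arm if 1:1 allocation holds in the subset.

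**Assumptions.** Room temperature is uniform over 21-25 °C and independent between visits. Mean finger temperature moves 0.25 to 1.0 °C per 1 °C of room. All other variation in the change has an SD of 2 to 4 °C.

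**Room difference between visits.** Variance at one visit: 4²/12 = 1.33. Difference of two visits: 2 × 1.33 = 2.67, SD 1.63 °C. Standard error of the chance difference between arms: 1.63 × √(2/25) = 0.46 °C.

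**Share of the variance of change due to the room**, from slope² × 2.67 / (slope² × 2.67 + SD²):

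| Slope (°C per °C) | SD 2 | SD 3 | SD 4 |
|---|---|---|---|
| 0.25 | 4% | 2% | 1% |
| 0.5 | 14% | 7% | 4% |
| 1.0 | 40% | 23% | 14% |

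The range is about 1% to 40%, for mean finger temperature between visits only.

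**If rooms are alike at both visits.** A subject would ordinarily return to the same site. With an assumed correlation of 0.5 between visits, the variance of the difference halves to 2 × 1.33 × (1 − 0.5) = 1.33. The extremes become 0.0625 × 1.33 / (0.083 + 16) = 0.5% and 1.33 / (1.33 + 4) = 25%.

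**What adjustment could gain.** With 25 per arm, two-sided 0.05 and 80% power, the smallest detectable difference is 0.81 SD. A covariate explaining a share R² of the residual variance multiplies the standard error by √(1 − R²):

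| R² | Detectable difference (SD) | Power at 0.81 SD |
|---|---|---|
| 0 | 0.81 | 80% |
| 5% | 0.79 | 82% |
| 10% | 0.77 | 84% |
| 20% | 0.72 | 88% |
| 30% | 0.68 | 92% |

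The shares in the first table are of the raw change. After adjustment for baseline they would differ somewhat, so the two tables connect only approximately.

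**Within-day endpoints.** Appendix 3 allows about 120 minutes after the first challenge before dosing, and the second challenge comes 180 minutes after dosing: 120 + 180 = 300 minutes, about five hours. Drift is possible in a room that is only monitored, but the documents give nothing from which to size it.

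**Log-scale endpoints.** A slope in °C per °C does not carry over to LN(AUC) or LN(maximum), so no share is given for them. Taking logs does not by itself remove an ambient effect.

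**The case against.** The strongest reply is that the planned ANCOVA is already valid and that the design limits the problem. Most of this stands.

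- **Validity.** A reader might infer that a warmer room in one arm would pass for a drug effect. The documents do not support that. Allocation is randomised and blinded, so a chance room imbalance is part of the residual error and is already reflected in the standard error and p-value. A shift common to both arms cancels.
- **Breadth.** A reader might also take the problem to be differences between visits, or seasons, across all four endpoints. Two of the four lie within Visit 2, and neither document gives seasonal data. Appendix 5 also stops short of saying that room temperature does affect the data; it is recorded to see whether it does.
- **Control by design.** Acclimatisation and rewarming at 23 ± 2 °C limit the spread, and DDD probably cancels part of any ambient shift (a judgement; the documents do not say so). But no limit is stated for a monitored room, and no rule covers a session outside the range. SAP 2.3 lists non-compliance with procedures as a possible per-protocol exclusion, but SAP 3.4 ties that set to effects on the primary endpoint, so it offers these analyses little protection.
- **Standing of the endpoints.** They are labelled secondary in the objectives, but SAP 5.3 places them under exploratory endpoints, outside the testing hierarchy and with nominal p-values. This limits the impact.
- **Availability.** Appendix 5 does not say how often room temperature is recorded. The visit schedules, the assessment table in Appendix 8 and the SAP name no such variable. Whether usable values reach the database must be checked.

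**Conclusion.** The point holds as one of precision. A measurement that treatment cannot affect is recorded for its possible influence on the thermography data, and no planned blood-flow analysis uses it. It matters mainly for mean finger temperature, LN(AUC) and LN(maximum), and less for DDD.

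For mean finger temperature between visits, the avoidable share of variance is about 1% to 40% under an assumed slope, an assumed SD and independent rooms spread evenly over the full tolerance; rooms that resemble each other across visits lower it. The gain from adjustment could be trivial or material, and the documents cannot settle which. They do not support a claim of bias or type I error inflation. This is a cheap improvement of low impact.

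**What to change.** In SAP 5.3.4 to 5.3.7, before unblinding:

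1. Prespecify an ANCOVA that adds the recorded room temperature at the baseline and follow-up assessments as covariates, or their difference if one term is preferred. For 5.3.5, use the room temperature averaged over the post-IMP window. It should stand at least as a sensitivity analysis beside the planned model.
2. Summarise room temperature by visit and arm.
3. Add a sensitivity analysis that excludes sessions recorded outside 21-25 °C.

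First confirm that room temperature is captured per session and will reach the analysis database.

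The cost is SAP text and one or two degrees of freedom. With about 50 subjects the planned model uses five parameters (intercept, two for stratum, treatment, baseline), leaving 50 − 5 = 45 residual degrees of freedom, or 43 with two covariates. Any subject without a recorded room temperature drops out of the adjusted analysis. SAP 2.1 has the plan finalised before database lock and unblinding, which is the time to do this; added later, the adjustment would look data-driven.
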